Study protocol and statistical analysis plan

Evaluation of the course and effectiveness of conservative therapy in patients with Achilles tendinopathy

NCT number: NCT05702918

Date: March 28, 2022

(Date of approval of the project by the ethics committee)

Study design and description

This work is designed as a randomized clinical trial, in which the effects of a protocol of 12-week resistance training loading the Achilles tendon and low-energy focused extracorporeal shock wave therapy (ESWT) in patients with Achilles tendinopathy (AT) will be monitored. It is estimated that at least 40 patients will participate, randomly divided into two groups. Group A will be instructed to perform a training protocol in combination with ESWT according to selected parameters. Group B only completes the same training protocol.

The research within one patient will last a total of 26 weeks from the initial to the final examination and will include several control measurements: at 6, 12, and 26 week from the beginning of therapy. Potential participants will be selected based on the recommendation of a specialist doctor and their suitability will be assessed according to the inclusion criteria. They will then be invited to an initial examination. This will include an objective examination by a physiotherapist, a subjective assessment by the patient and an ultrasonographic (USG) examination followed by a micromorphological analysis using special software. At the end of the initial examination, the participant will be randomly assigned to group A or B. Group A will follow resistance training protocol and receive ESWT. Group B will follow resistance training only. The study program for a specific participant will depend on the assigned group.

Patient selection

Inclusion criteria: age 18–50 years; localized Achilles tendon pain limiting daily or sports activity; clinical manifestation of AT confirmed by a clinician; and unilateral symptoms.

Exclusion criteria: professional or high-volume recreational sports (>4 sessions/week, >1h each); contraindications to ESWT according to International Society for Medical Shockwave Treatment (ISMST) guidelines at <https://shockwavetherapy.org>; previous symptomatic mechanical tendon injury (partial/complete rupture); history of contralateral AT; neurological, metabolic, oncologic, or systemic disease (e.g., diabetes, neuropathy, lupus, spondyloarthritis, rheumatoid arthritis); AT-specific treatment within the past 6 months; or use of anticoagulants or statins.

Initial and final examination

During the initial and final examinations, the several tasks to the patient will be performed. Firstly the anamnestic data will be collected, then the area of greatest pain will be localized by palpation.

Secondly, the patient will be asked to complete a validated Victorian Institute of Sports Assessment - Achilles (VISA-A) questionnaire, which assesses the subjectively perceived severity of the disease and partly its impact on the quality of normal daily or sports activities.

The patient's maximal pain will be assessed using a standardized numerical rating scale (NRS) of pain. The patient will be asked about the morning and maximum pain that could be caused by various factors.

Lastly, the ultrasonographic (US) examination and subsequent software analysis using Spatial Frequency Analysis (SFA) of patient's AT in both legs will be performed. This examination is described in the following chapter.

Both, initial and final examinations in each patient will be performed by only one person (the investigator of the study).

Ultrasonographic examination

Ultrasound imaging will be performed by the same experienced examiner using a linear probe (L12-3E, 12 MHz) on a Mindray DC-70 system in MSK preset (B-mode). The participant will be placed in the prone position with the knee in an extended position and the ankle passively maintained in neutral position. The midportion of the Achilles tendon will be evaluated from the

myotendinous junction to the upper border of calcaneus. The probe will be placed as parallel to the tendon fibers as possible, and the image capture will be always carefully performed to ensure optimal image quality and minimize movement artifacts.

The values of anteroposterior tendon width at the anteroposterior widest point will be collected using the measuring instruments included in USG machine.

After that, the preset will be changed to the specific setting, and three pictures will be saved in long axis for subsequent micromorphological analysis using SFA. SFA is a non-invasive, specialized method which analyzes the US image *in vivo*. In particular, it analyzes the anisotropic B-mode speckle pattern arising from within a tissue type in the spatial frequency domain and is capable of detecting and comparing collagen fascicles organization, spacing, and density across various parameters. Mean of those three values will be used for statistical analysis.

ESWT application

The low-energy focused ESWT will be applied using the BTL-6000 FSWT machine with piezoelectric generator and a coupling pad which modulates penetration depth to 0-35 mm. The setting is chosen based on ISMST guidelines (<https://shockwavetherapy.org>): Energy Flux Density (EFD) between 0.10-0.15 mJ/mm² due to patient tolerance, frequency at 5 Hz. A total of 2000 shocks will be applied semi-statically to the most US defined pathological tendon area using a contact gel. The set parameters will not change during the study and will remain the same for each patient.

Data analysis

The normality of the data distribution will be determined by calculating the Shapiro-Wilk p value. Independent t-tests (or Mann Whitney U tests for non-parametric) will be performed for each parameter to compare baseline values between groups. In addition, paired t-tests (or Wilcoxon tests) will be performed for each parameter, evaluated in each group separately between baseline and final values. To reach effect size, Cohen's d will be calculated for paired t-tests and biserial rank correlation for non-parametric Wilcoxon test.

Intergroup statistical significance between baseline and follow-up values of morphological parameters will be evaluated using two-way ANOVA with repeated measures or non-parametric Friedman test. Statistical significance is set to $p < .05$.

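### Both arms train, so randomisation identifies only the added effect of ESWT; the within-arm baseline-to-final tests cannot show that training works and should be labelled descriptive

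*Combined protocol and SAP*

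**What the plan says.** The section Study design and description gives the aim as monitoring "the effects of a protocol of 12-week resistance training loading the Achilles tendon" together with low-energy focused ESWT. The title refers to both the course and the effectiveness of conservative therapy. On treatment, "Group A will be instructed to perform a training protocol in combination with ESWT according to selected parameters", while "Group B only completes the same training protocol". No untreated, wait-list or non-training arm is described. On size, "It is estimated that at least 40 patients will participate, randomly divided into two groups". Each patient is followed for 26 weeks, with measurements at 6, 12 and 26 weeks.

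The section Data analysis plans paired t-tests or Wilcoxon tests for each parameter, "evaluated in each group separately between baseline and final values". Cohen's d or a rank-biserial correlation accompanies these tests, and no other test in the plan has an effect size. A between-group analysis (two-way repeated-measures ANOVA or Friedman) is named for the morphological parameters only.

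Patient selection requires "clinical manifestation of AT confirmed by a clinician; and unilateral symptoms", and a history of Achilles tendinopathy on the other side is an exclusion. At the initial and final examinations, ultrasound and spatial frequency analysis (SFA) of the "AT in both legs will be performed". Data analysis mentions no comparison between legs.

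**The concern.** The aim names two interventions, but the design varies only one. Training is the same in both arms and cancels in the A-versus-B contrast, so that contrast says nothing about whether training works.

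This leaves the paired tests as the only planned analysis that could speak to training, or to either regimen as a whole. Patients enter because pain limits their activity, and no run-in or repeated baseline is described. Some improvement over 26 weeks would therefore be unsurprising without any treatment effect. A p value below 0.05 with a Cohen's d beside it is easily read as evidence of effectiveness, and the plan has no sentence to prevent that reading. For VISA-A and NRS the risk is greater, because the within-arm test is the only follow-up test specified for them.

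**Working it through.** **No figure to reproduce.** The plan gives at least 40 patients without an effect size, SD, power or allocation ratio, so its sample size cannot be re-derived. The calculation below shows the size of the attribution problem.

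**Inputs**
- n = 20 per arm: 40 patients in two groups, 1:1 assumed because the ratio is not stated.
- Alpha 0.05 from Data analysis, two-sided assumed.
- True effect of training: zero, by construction.
- Background change δ, in units of the SD of the change score: 0.3, 0.5 and 0.8. These are assumptions; the documents give no value.

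**Within-arm paired t-test.** The statistic follows a noncentral t distribution with n − 1 = 19 degrees of freedom and noncentrality δ√n. The critical value is 2.093.

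| δ | δ√20 | P(one arm significant) | P(at least one of two arms significant) = 1 − (1 − p)² |
|---|---|---|---|
| 0.3 | 1.342 | 0.247 | 0.433 |
| 0.5 | 2.236 | 0.5645 | 0.810 |
| 0.8 | 3.578 | 0.924 | 0.994 |

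A simulation of 20,000 trials agrees: at least one arm was significant in 0.437, 0.810 and 0.995 of them.

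**Between-arm comparison of change.** With the same background change in both arms and no effect of ESWT, the simulated rejection rates were 0.051, 0.051 and 0.050. Background change cancels, which is why this contrast can carry a conclusion and the within-arm tests cannot.

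**Would the unaffected tendon rescue the within-arm analysis?** The same simulation tested the affected-minus-unaffected change in one arm of 20, with the two legs assumed uncorrelated and equally variable. The SD of the side difference is then √2 times that of one leg.

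| δ | Change is drift shared by both legs | Change is recovery of the affected tendon only |
|---|---|---|
| 0.3 | 0.050 | 0.148 |
| 0.5 | 0.050 | 0.318 |
| 0.8 | 0.049 | 0.671 |

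The right-hand column agrees with theory: noncentrality (δ/√2)√20 = 0.949, 1.581 and 2.530 gives 0.147, 0.324 and 0.670. The side difference removes drift common to both legs. It does not remove recovery confined to the diseased tendon.

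**The case against.** The strongest reply is that this is an ordinary add-on trial. Comparing training plus ESWT with training alone is a valid question, and choosing it is no error. The title also names the course of the condition, which within-arm change describes naturally, and the aim says only that effects will be monitored. No sentence says that a significant paired test will be reported as proof that training works. All of this stands. It limits the point to what may be concluded, but it leaves the paired tests unlabelled in a plan whose title also says effectiveness.

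The probabilities above are simply the power of a paired t-test at assumed shifts. When patients have changed, the null of no mean change is false and rejecting it is correct. A reader might infer an inflated type I error; the documents do not support that. The fault would lie in attribution.

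A reader might also infer that the other tendon supplies the missing control. It does not. It is no reference for VISA-A or NRS, it leaves natural recovery in place, and the documents do not say whether training loads one leg or both. Nor may side differences be assumed available at every visit: scanning of both legs is stated only for the initial and final examinations.

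Finally, the plan already limits drift by using the same examiner, probe and scanner and by averaging three SFA images. Entry uses no width or SFA threshold, so regression to the mean is a weaker worry for morphology than for pain. These controls reduce drift without excluding it, and they do not touch natural recovery.

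**Conclusion.** The point holds as a limit on conclusions. Randomisation identifies the added effect of ESWT and nothing else, and the plan's only evidence on training cannot separate it from recovery, regression to the mean or drift. Under an assumed background change of 0.3 to 0.8 SD and no training effect, an arm of 20 would show a significant improvement in about 25% to 92% of cases. The range rests on 1:1 allocation, two-sided testing and assumed shifts, and says nothing about how likely such shifts are in these patients.

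A reader might go further and infer that the trial is invalid without an untreated arm. The documents do not support that: the A-versus-B contrast answers the add-on question whatever the common background change. The point should be settled before analysis because the remedy needs no new patients, treatments or visits.

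**What to change.** In Data analysis, state three things:

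1. The within-arm baseline-to-final tests, with their Cohen's d and rank-biserial values, describe course only. They will not be reported as effectiveness of training or of either regimen.
2. The only effectiveness conclusion is the between-arm added effect of ESWT.
3. That between-arm comparison of change, with its effect size, is made for VISA-A and NRS as well as for the morphological parameters. Without this, the first two statements would leave the patient-reported outcomes with no effectiveness analysis.

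Optional supplement: for tendon width and SFA, report the change in the affected-minus-unaffected difference between the initial and final examinations, beside the raw change in the affected tendon. Label it a check on shared measurement drift only. State that it does not remove natural recovery of the affected tendon, carries the measurement error of two tendons, and may be distorted if training loads both legs.

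Cost: a few sentences, between-arm analyses of data already collected and, if the supplement is adopted, one derived variable from scans already planned. The price is a weaker claim about training, which is all this design can support.

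### VISA-A and pain scores have no planned time-course, end-of-training or between-arm follow-up analysis, although measurements are scheduled at weeks 6, 12 and 26

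*Combined protocol and SAP*

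**What the plan says.** The title of the combined protocol and SAP is "Evaluation of the course and effectiveness of conservative therapy in patients with Achilles tendinopathy". *Study design and description* says the trial will monitor "the effects of a protocol of 12-week resistance training loading the Achilles tendon", together with shock wave therapy in one arm. On timing it says: "The research within one patient will last a total of 26 weeks from the initial to the final examination". It adds that this period "will include several control measurements: at 6, 12, and 26 week from the beginning of therapy".

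The outcomes are set out in *Initial and final examination*, which opens: "During the initial and final examinations, the several tasks to the patient will be performed". VISA-A, the NRS for morning and maximum pain, and ultrasound with spatial frequency analysis (SFA) are all placed there. No section describes the content of the week-6 and week-12 measurements.

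*Data analysis* has three components:
- Independent t-tests (or Mann-Whitney) compare the arms at baseline.
- For change over time, "paired t-tests (or Wilcoxon tests) will be performed for each parameter, evaluated in each group separately between baseline and final values".
- A two-way repeated-measures ANOVA (or Friedman test) compares the arms from baseline to follow-up. It is confined to morphological parameters, and the follow-up visits are not named.

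**The concern.** The schedule and the title point to a trial that follows recovery over time. The outcome section and the main testing rule describe a trial that looks at the start and the end. Week 12 is the natural point to ask what the training programme achieved with and without shock wave therapy, and nothing in the analysis names it.

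The gap matters most for VISA-A and NRS, the outcomes that patients feel. Their only follow-up test is made inside each arm. A significant change in one arm and a non-significant change in the other is not a comparison of the arms, so the randomised question goes unanswered for pain and function.

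A week-26 result also reflects whatever happened after training ended. The documents do not describe exercise, sport or other treatment in that period. If the arms differed at week 12 and had converged by week 26, the week-26 data alone could not separate that pattern from no effect at all. For morphology, leaving the visits unnamed lets the time points be chosen after the data have been seen.

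**Working it through.** The plan gives no figure on this point to reproduce. Its sample size, at least 40, comes with no effect size, standard deviation, power or dropout rate. The check is therefore a visit-by-visit reading.

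**Inputs**
- Visits: baseline and weeks 6, 12 and 26 (*Study design and description*).
- Training length: 12 weeks (same section).
- Final examination: week 26, because participation runs 26 weeks from the initial to the final examination (same section).
- Outcomes and the occasions described for them (*Initial and final examination*).
- Tests and the values they use (*Data analysis*).

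**Step 1. Map visits to outcomes and tests**

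| Week | Outcome content described | Paired within-arm test | Between-arm follow-up test, VISA-A and NRS | Between-arm repeated-measures test, morphology |
|---|---|---|---|---|
| 0 | Full set | Yes | Not applicable (baseline comparison only) | Yes |
| 6 | Not stated | No | None | Not stated |
| 12 (end of training) | Not stated | No | None | Not stated |
| 26 (final) | Full set | Yes | None | Implied, not named |

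**Step 2. Count for the patient-reported outcomes**
There are three measures (VISA-A, morning NRS, maximum NRS) and three follow-up visits, so 3 × 3 = 9 between-arm follow-up comparisons could be made. The plan specifies 0. The within-arm tests use 1 of the 3 follow-up visits.

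**Step 3. Timing**
The final examination falls 26 − 12 = 14 weeks after a 12-week programme ends, and 14 / 26 = 0.54, or 54% of follow-up. This assumes that training starts close to the initial examination. It applies to training only, because the documents give neither the number nor the timing of the shock wave sessions.

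**Step 4. Morphology**
The paired tests are tied to the final value. The repeated-measures analysis refers to follow-up without naming a visit. Weeks 6 and 12 can be in that model only if ultrasound is done then, and the text neither says that it is nor rules it out.

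**The case against.** The strongest counter-argument is that silence is not exclusion. The outcome section never says that its measures are taken only at the initial and final examinations, and a scheduled control measurement presumably measures something. Week 26 is itself listed among the control measurements and has the full outcome set. *Data analysis* also changes its wording between the paired tests and the repeated-measures analysis. The non-parametric fallback there is Friedman, conventionally used for three or more related measurements, which hints that weeks 6 and 12 were meant to enter.

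This stands, and it limits the point. A reader might infer that weeks 6 and 12 yield no data, that the ANOVA can hold only week 26, or that the trial assesses neither the course nor the end-of-treatment effect. The documents do not support any of these: the measurements are scheduled, and the morphological model may include them.

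The objection does not reach VISA-A and NRS. Even if both are collected at every visit, the stated analysis uses only their baseline and final values, within each arm.

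It is also fair to say that week 26 is a legitimate main time point if the sponsor wants to know whether benefit lasts. Nothing in the documents makes week 12 primary.

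**Conclusion.** The point holds in a limited form. For VISA-A and NRS, the plan followed as written has no time-course analysis, no end-of-training analysis and no between-arm analysis at follow-up: 0 of 9 possible measure-by-visit comparisons are specified. For morphology, the between-arm model exists but its visits are ambiguous.

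This goes beyond missing detail, because the testing rule as it stands leaves the title's question about course unaddressed for pain and function. It is a change that should be made and is cheap to make; it does not show that the trial is unable to describe recovery. The conclusion rests on reading the final examination as week 26, which the protocol states, and on taking the listed tests as the complete analysis. A reader might want the cost of testing at week 26 expressed as lost power. The documents give no effect sizes, no standard deviations and no follow-up two-sample test from which to derive one.

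**What to change.** 1. In *Initial and final examination*, require VISA-A and both NRS items at weeks 6 and 12, as well as at baseline and week 26, in both arms. Ultrasound with SFA at week 12 is optional. State explicitly whether it is done at weeks 6 and 12.
2. In *Data analysis*, replace the rule "evaluated in each group separately between baseline and final values" with an analysis that uses all scheduled visits and estimates the between-arm difference in change from baseline at each visit, for VISA-A and NRS as well as morphology. A linear mixed model with arm, visit and their interaction, adjusted for baseline, would do this. Name the visits that enter it for each outcome.
3. Name one main time point in advance, week 12 or week 26 at the sponsor's choice, with a sentence giving the reason. Report the other visits as supporting information on course or durability.

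The cost is a few minutes per patient at visits already scheduled, revised analysis wording, and more time points to report. If the optional week-12 ultrasound is adopted, it adds one extra scanning session per patient, about 40 at the planned minimum sample size.

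### VISA-A and pain scores follow history-taking and palpation by one investigator for whom no blinding is described; collecting them first would remove an avoidable examiner influence

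*Combined protocol and SAP*

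**What the plan says.** The section Initial and final examination sets out a sequence:

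- First: "Firstly the anamnestic data will be collected, then the area of greatest pain will be localized by palpation".
- Next: "Secondly, the patient will be asked to complete a validated Victorian Institute of Sports Assessment - Achilles (VISA-A) questionnaire".
- Then the pain NRS: "The patient will be asked about the morning and maximum pain that could be caused by various factors".
- At the end: "Lastly, the ultrasonographic (US) examination and subsequent software analysis using Spatial Frequency Analysis (SFA").

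On who does this, the same section says: "Both, initial and final examinations in each patient will be performed by only one person (the investigator of the study").

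The section Study design and description gives the timing of allocation: "At the end of the initial examination, the participant will be randomly assigned to group A or B". It describes the comparator as follows: "Group B will follow resistance training only". No sham shock wave treatment is described.

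The plan does not say whether the investigator is blinded, who delivers the shock wave treatment, whether the NRS is answered aloud or on paper, or whether VISA-A and NRS are collected at weeks 6 and 12.

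**The concern.** VISA-A and the NRS are the only symptom scores described. Both depend on what patients report, and such reports can be coloured by a conversation or an examination that has just taken place. Under the stated order, the patient has gone through the history with the investigator and had the tendon palpated before giving either score.

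At the initial examination nobody can know the arm, because it has not been assigned. At the final examination it has been. A patient who knows the treatment received and is asked about the past months may well mention it. The order of tasks thus gives the investigator a ready way to learn the arm just before the symptom scores are taken. What is at stake is whether some of the recorded change in symptoms reflects that encounter rather than the treatment.

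**Working it through.** This is mainly a reading of the text. The plan has no figure of its own to reproduce here: at least 40 patients is stated without an effect size, SD or power.

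**Step 1. Is the order really fixed?** Yes. The three sequence words (first, second, last) tie history and palpation to the start, VISA-A after them and ultrasound to the end. The NRS is described between VISA-A and ultrasound. The section covers the initial and final examinations only.

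**Step 2. Compare the two visits.**

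| | Initial examination | Final examination |
|---|---|---|
| Relation to randomisation | Before | After |
| Patient knows the arm | No | Yes (no sham described) |
| Investigator knows the arm | Cannot | Not stated; no blinding described |
| History precedes symptom scores | Yes | Yes |
| Same investigator | Yes | Yes |

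The procedure is the same at both visits, but the information available to the investigator is not. An examiner influence that depends on the arm can arise only at the final visit, so it would not be subtracted out by the baseline value.

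**Step 3. When is the influence differential?** Let e be the shift in a symptom score caused by the preceding history and palpation.

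- If e is the same in both arms, the between-arm bias is e − e = 0.
- If e is also the same at both visits, the within-arm change is unbiased as well.
- If the arm is known, or the conversation runs differently in the two arms, the between-arm bias is e(A) − e(B), which need not be zero.

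**Step 4. Which planned analysis is exposed?** Data analysis specifies a between-group follow-up comparison for morphological parameters only. For VISA-A and NRS, the baseline-to-final tests stated are paired tests within each group. A shift that differs between visits goes straight into those changes, with no control arm to subtract it.

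**Step 5. How exposed is each score?** VISA-A is completed by the patient. The NRS items concern morning and maximum pain, not pain at that moment. Direct carry-over from palpation is therefore limited. The influence of conversation is not limited in the same way, and the NRS is the more exposed if it is asked face to face.

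**Step 6. Scale, by assumption only.** Assume 20 per arm (equal split of 40), two-sided 5%, no true effect, and a shift of δ SD in one arm at the final visit. The rejection probability is P(|T| > critical value), with T noncentral t:

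- Between groups (a test the plan does not specify for these scores): 38 df, noncentrality δ/√(2/20) = 3.16δ.
- Paired within that arm: 19 df, noncentrality δ√20 = 4.47δ, with δ in SDs of change.

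| Assumed δ | Between groups | Paired, within arm |
|---|---|---|
| 0 | 5% | 5% |
| 0.1 | 6% | 7% |
| 0.2 | 9% | 14% |
| 0.3 | 15% | 25% |
| 0.5 | 34% | 56% |

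The documents give no basis for choosing any row. The paired column is also artificial, since both arms train and some change is plausible anyway; there the shift would distort the estimated change.

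**The case against.** The strongest reply is that the underlying gap is undescribed blinding, and that task order only follows from it. The sequence is the same in both arms and at both visits, so any effect of order alone is non-differential. That stands, and the point is limited accordingly.

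A reader might go further than the text allows in four ways:

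- *That the investigator knows the arm at the final visit.* The documents do not say so. They describe no blinding, and history-taking with an unblinded patient makes disclosure likely. That is an inference.
- *That palpation is performed so as to provoke pain, at an uncontrolled pressure, and that the NRS is asked orally.* The text says only that palpation locates the area of greatest pain. Palpation is not described as a scored outcome, so a missing pressure standard is not a defect in an outcome. The mode of the NRS is not stated.
- *That the bias amounts to a set fraction of the detectable effect.* That needs an NRS shift and an SD that the documents do not supply. It also measures them against a between-group test that the plan does not specify for these scores.
- *That reordering would make the symptom outcomes unbiased.* Patients who know their arm bring that knowledge to a form completed on arrival too.

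What the reply does not answer is that the order is a stated choice, that it places the likely moment of disclosure ahead of the symptom scores, and that nothing in the palpation or the ultrasound requires them to come before the forms.

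**Conclusion.** The point holds in limited form. At the initial and final examinations the symptom scores follow history and palpation by a single investigator with no described blinding. At the final visit, after randomisation and without a sham, that investigator is likely to learn the arm first. This is an avoidable route for examiner influence on VISA-A and the NRS.

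Its size cannot be calculated from the documents and could be zero. A bias between arms requires that the arm becomes known or that the interaction differs by arm. The conclusion rests on two assumptions: that the printed sequence is followed, and that the investigator is not shielded from the allocation by some arrangement the plan leaves out. It is a minor to moderate point, worth acting on because the remedy is nearly free.

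**What to change.** In the section Initial and final examination, put the self-reported scores first. On arrival, the patient completes VISA-A and written NRS items for morning and maximum pain, alone, before history, palpation or any discussion of treatment. The forms are closed before the examination begins. Apply the same rule at weeks 6 and 12 if these scores are collected then. State also whether the investigator is blinded to the arm.

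The cost is a sentence or two in the procedure, with no extra staff or visits. Any patients already assessed in the present order should be noted, since their baseline and final scores may have been taken under different orders. The change removes only the same-visit examiner component. The report should still acknowledge that patients knew their treatment.

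### The plan describes no masking of the follow-up examiner or image reader, and tendon width is read live at a point the operator locates

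*Combined protocol and SAP*

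**What the plan says.** Under Study design and description, two groups are planned: "It is estimated that at least 40 patients will participate, randomly divided into two groups". Allocation follows the baseline assessment: "At the end of the initial examination, the participant will be randomly assigned to group A or B". The comparator has no sham: "Group B will follow resistance training only".

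Initial and final examination gives the order of work. It opens with "Firstly the anamnestic data will be collected, then the area of greatest pain will be localized by palpation", goes on to VISA-A and the pain ratings, and ends with ultrasound: "Lastly, the ultrasonographic (US) examination and subsequent software analysis using Spatial Frequency Analysis (SFA"). Both legs are scanned. The same section says: "Both, initial and final examinations in each patient will be performed by only one person (the investigator of the study").

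Under Ultrasonographic examination, "Ultrasound imaging will be performed by the same experienced examiner". Patient position, knee and ankle position and the limits of the scanned segment are fixed. Width is then taken as follows: "The values of anteroposterior tendon width at the anteroposterior widest point will be collected using the measuring instruments included in USG machine". The preset is changed after that, and three long-axis pictures are saved for SFA, whose values are averaged.

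Under Data analysis, the follow-up tests are within-group comparisons of baseline with final values for each parameter, plus one between-group analysis for the morphological parameters (two-way repeated-measures ANOVA, or Friedman). The significance level is 0.05.

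The text contains no statement on masking, coded images or an independent reader.

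**The concern.** Width depends on the operator: someone must find the widest point and place the callipers. If that person knows the group at follow-up, small unconscious differences in searching or placement can differ by arm. The resulting shift could go in either direction. It would look exactly like an effect of ESWT, and no planned analysis could separate the two.

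The stakes are high relative to the rest of the plan, because the morphological comparison is the only stated follow-up test that uses the randomisation. As written, width also could not be re-read masked later, since the only pictures said to be saved are for SFA, taken after the width measurement and under a different preset.

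**Working it through.** **1. Could the examiner learn the group?** The documents leave two routes open.
- *At allocation.* Randomisation falls at the end of an examination done by the investigator alone. The plan does not say who reveals the result.
- *At the final visit.* The examiner takes the history and collects questionnaire and pain answers before scanning. With no sham described, the patient can tell whether ESWT was given.

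The plan does not say who gives ESWT, so this cannot be counted as a third route.

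**2. Which readings are exposed?**
- *Baseline:* protected, because it precedes allocation.
- *Follow-up width:* most exposed, being a live reading at a located point with no repeat reading or saved width frame described.
- *SFA:* less exposed. It is described as software analysis averaged over three saved pictures, so exposure is mainly at image capture and at any manual step such as region selection, which the plan does not mention.

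**3. What would a given bias do?** The plan has no figure to reproduce: it gives no SD, reliability, bias size or sample-size calculation. What follows is an illustration.

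Inputs: at least 40 patients and a level of 0.05 (from the plan); 20 per arm, a two-sided test, two ultrasound visits and the bias b in SDs of change (all assumed).

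With two visits, the group-by-time F on 1 and n₁+n₂−2 df equals the square of the two-sample t on change scores, so no correlation needs to be assumed. With no true effect, t is noncentral with λ = b·√(n₁n₂/(n₁+n₂)), and the false-positive rate is P(|t| > critical value).

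| Arms | √(n₁n₂/(n₁+n₂)) | b | λ | False-positive rate |
|---|---|---|---|---|
| 20/20 | √10 = 3.162 | 0.1 | 0.316 | 6.1% |
| 20/20 | 3.162 | 0.212 | 0.670 | 10.0% |
| 20/20 | 3.162 | 0.3 | 0.949 | 15.2% |
| 24/16 | √9.6 = 3.098 | 0.3 | 0.930 | 14.8% |
| 30/30 | √15 = 3.873 | 0.3 | 1.162 | 20.8% |

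For 20/20, a simulation of 200,000 runs gave 4.96% at b = 0, 6.0% at 0.1 and 15.0% at 0.3. An uneven split changes little. A larger sample makes the error rate worse, because bias does not shrink with n. The equivalence does not carry over to more than two visits, and the Friedman option is not covered.

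**4. Size of the remedy.** With an assumed three width frames per leg: 40 patients × 2 legs × 2 visits × 3 = 480. At an assumed 1 to 2 minutes each, that is 480 to 960 minutes, or 8 to 16 hours. SFA adds 480 files to code if its three pictures are saved per leg, making 960 in all. The plan lists control measurements at 6 and 12 weeks but does not say whether they include ultrasound. If they do, all these counts and the reading hours double.

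**The case against.** *Silence is not unmasking.* This is correct. A reader might infer that the examiner knows the group, or that the person who measures also treats. The documents say neither. What stands is narrower: the described procedure contains no barrier.

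*The examination is standardised and one examiner gives consistency.* Also true. Fixed positioning, a bounded segment and a maximum-width rule limit operator latitude, and a single examiner is a reasonable choice. Neither of these masks the reading.

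*The remedy is imperfect.* This largely stands.
- If the examiner already learned the group at allocation, scanning before questioning masks nothing, so the reveal itself has to be handled.
- A few stored frames may miss the true maximum that live scanning would find.
- The same reader may recognise images.
- Coded reading does not mask probe placement or the choice of frames. For SFA, where the exposure is mainly at capture, coding helps only with a manual step, if there is one.

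*The bias sizes are invented.* They are assumptions, with no link to millimetres or reliability. They show how sensitive the test is to a given shift, not what would happen in this trial.

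**Conclusion.** The point holds as a gap in the described procedure. No masking protects the follow-up morphological readings, and the written sequence (allocation at the end of the investigator's own examination, questioning before scanning, live width reading) leaves the one stated between-group comparison open to observer bias. Width is the main exposure and SFA a lesser one.

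The size of any bias is unknown. False-positive rates of about 6% to 15% apply only under assumed shifts of 0.1 to 0.3 SD of change, 20 per arm, two ultrasound visits and the ANOVA. It would go too far to conclude that the width results will be biased or will favour ESWT: the documents show neither knowledge of group nor a direction. If masking is in fact planned, stating it would answer much of the point. This is a recommended improvement to the plan, held with medium confidence.

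**What to change.** Keep the single examiner and make four changes.

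1. Where possible, have another member of the existing team reveal allocation after the initial examination. Otherwise report that the examiner knew the group.
2. At follow-up, scan before history, palpation and questionnaires, and ask patients not to disclose their group.
3. Keep the on-machine width, but also save calibrated long-axis frames at and around the widest point before callipers are placed. After the last visit, the same examiner re-reads them in random order under random codes, without name, group, visit or date. A colleague holds the key until data lock. Use the masked width in the between-group comparison and report its agreement with the on-machine value.
4. Run SFA on coded files. This matters only for any manual step.

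**Cost.** No extra assessor or patient procedure is needed. The work is saving the frames, a renaming script, the reading time worked out above, and colleagues to reveal allocation and hold the key; their availability is assumed. SFA processing time is not included. The masked width is available only at the end of the study, and it is measured off the machine.

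**To report as limitations.** Stored frames may miss the maximum, images may be recognised, and acquisition may remain unmasked. VISA-A and NRS are not protected, because patients without a sham know their group.
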